14.2.3 Formulation and Preparation

Avelumab drug product is a sterile, clear, and colorless concentrate for solution presented at concentration of 20 mg/mL in European Pharmacopeia (Ph. Eur.) and United States Pharmacopeia (USP) type I glass vials closed with a rubber stopper and sealed with an aluminum Flip Off® crimp seal closure.

Each single-use vial contains 200 mg of avelumab as a preservative-free acetate-buffered solution (pH 5.2) containing Mannitol, and Polysorbate 20 (Tween 20).

For avelumab drug product, only excipients that conform to the current Ph. Eur. and/or the current USP are used.

14.2.4 Stability and Storage

Supplies must be stored in a secure, limited-access location under the storage conditions specified on the label. Receipt and dispensing of trial supplies must be recorded by an authorized person at the trial site. Supplies may not be used for any purpose other than that stated in the protocol.

Avelumab drug product must be stored at 2°C to 8°C until use. Store diluted solution at room temperature up to 77°F (25°C) for no more than 4 hours from the time of dilution. *OR* Under refrigeration at 36°F to 46°F (2°C to 8°C) for no more than 24 hours from the time of dilution. If refrigerated, allow the diluted solution to come to room temperature prior to administration. The storage condition is based on data from ongoing long-term stability studies with avelumab. Avelumab drug product stored at room (23°C to 27°C) or higher temperatures for extended periods of time might be subject to degradation. Avelumab drug product must not be frozen. Rough shaking of the solution must be avoided.

14.2.5 Administration Procedures

For administration in clinical trials, avelumab drug product may be diluted with 0.9% saline solution (sodium chloride injection) supplied in 250 mL infusion bags, alternatively, a 0.45% saline solution can be used if needed. The chemical and physical in-use stability for the infusion solution of avelumab in 0.45% or 0.9% saline solution has been demonstrated for a total of 24 hours at room temperature. However, from a microbiological point of view, the diluted solution should be used immediately. If not used immediately, it can be considered that the diluted product is sufficiently stable from a microbiological perspective for up to 8 hours when stored at ambient room temperature or up to 24 hours at 2°C to 8°C. The in-use storage times and conditions prior to administration are the responsibility of the user.

Prior to the preparation of the dilution for final infusion, allow each vial to equilibrate to room temperature. Use a disposable syringe equipped with a needle of suitable size to remove a volume of sodium chloride solution to be replaced by avelumab from the infusion bag and discard the removed solution. Use a new disposable syringe equipped with a needle of suitable size to inject a volume of avelumab drug product identical to the discarded volume of sodium chloride solution into the infusion bag. Gently invert the mixture 10 times. Infusion bags must not be shaken, in order to avoid foaming or excessive shearing of the protein solution. The preparation must be carefully inspected as it should result in a homogeneous looking clear solution, free of visible particles.

14.2.6 Returns and Reconciliations

Unused investigational products will be destroyed per routine pharmacy procedure.

16 APPENDICES

16.1 APPENDIX A: PERFORMANCE STATUS CRITERIA

ECOG Performance Status Scale		Karnofsky Performance Scale	
Grade	Descriptions	Percent	Description
0	Normal activity. Fully active, able to carry on all pre-disease performance without restriction.	100	Normal, no complaints, no evidence of disease.
		90	Able to carry on normal activity; minor signs or symptoms of disease.
1	Symptoms, but ambulatory. Restricted in physically strenuous activity, but ambulatory and able to carry out work of a light or sedentary nature (e.g., light housework, office work).	80	Normal activity with effort; some signs or symptoms of disease.
		70	Cares for self, unable to carry on normal activity or to do active work.
2	In bed <50% of the time. Ambulatory and capable of all self-care, but unable to carry out any work activities. Up and about more than 50% of waking hours.	60	Requires occasional assistance, but is able to care for most of his/her needs.
		50	Requires considerable assistance and frequent medical care.
3	In bed >50% of the time. Capable of only limited self-care, confined to bed or chair more than 50% of waking hours.	40	Disabled, requires special care and assistance.
		30	Severely disabled, hospitalization indicated. Death not imminent.
4	100% bedridden. Completely disabled. Cannot carry on any self-care. Totally confined to bed or chair.	20	Very sick, hospitalization indicated. Death not imminent.
		10	Moribund, fatal processes progressing rapidly.
5	Dead.	0	Dead.

16.2 APPENDIX B: ASSAY FOR ADCC

- Peripheral blood mononuclear cells (PBMCs) should be isolated by Ficoll-High-Paque Density Gradient Centrifugation.
- The viable cells should be viably frozen and stored in liquid nitrogen.
- The ADCC assay will be performed on the same occasion for all samples of a given patient.
- Vials of frozen cells will be thawed using standard procedures 18 hours before the assay in accordance with our experience with normal donors.
- 1.5 million of patient's PBMCs obtained before and on day 15 following IL-15 injection will be tested in aliquots as follows:
 - Tested alone
 - Tested with untreated PD-L1-expressing Raji cells and with PD-L1-expressing Raji cells coated with avelumab for 5 hours.
 - In addition, we may utilize an ATL cell line in addition to Raji cells. These cell populations will be stained with CD107, CD3, CD56 and CD94.

16.3 APPENDIX C: IL-15 DILUTION INSTRUCTIONS

All dose preparations will be performed in a laminar flow hood in compliance with all legal requirements and in accordance with guidelines of recognized organizations.

0.1% human serum albumin (HSA) in 5% dextrose in water, USP (D5W), or in 0.9% sodium chloride (NS) may be used for the dilutions listed below.

Please note: The dosing examples listed below are for the 147 mcg/0.3 mL in a 3mL vial size and dilution ONLY. The following dosing chart may be used as a reference, but doses should always be re-calculated at the time of preparation. In the future, different concentrations of IL-15 may be available and doses and dilutions will need to be recalculated.

Dose Level 1 (2 mcg/kg) and Dose Level 2 (4 mcg/kg)

To prepare an IL-15 dose for Dose Level 1 (2 mcg/kg):

1. Thaw vial(s) of IL-15, **147 mcg/0.3 mL (490 mcg/mL)** at room temperature.
2. Using a 27-gauge needle, slowly draw up the required dose in a 1 mL syringe. Doses should be rounded to the nearest 0.01 mL.
3. Add the calculated volume of diluted IL-15 to 0.1% HSA in D5W, or in NS, in a PVC or polyolefin bag.
4. Label the bag with a 4-hour beyond-use date. The infusion may be started within 4 hours at room temperature, or within 24 hours if bag was kept at 2-8°C. The infusion must be completed within 24 hours of initiation.

Administered dose = _____ kg (Patient's weight) X _____ mcg/kg (DL) = _____ **mcg**

Prepared dose = _____ mcg (Administered dose) + 10 mcg (Overfill dose) = _____ **mcg**

IL-15 volume = _____ mcg (Prepared dose) ÷ 490 mcg/mL (vial concentration) = _____ **mL**

Total infusion volume =

_____ mcg (Prepared dose) ÷ 1 mcg/mL (final infusion concentration) = _____ **mL**

Diluent volume =

_____ mL (Total infusion volume) - _____ mL (IL-15 volume) = _____ mL

[figure not shown]
Patient's weight	IL-15 volume (490 mcg/ml)		Diluent volume		Total infusion volume (1 mcg/ml)	
	2mcg/kg	4 mcg/kg	2 mcg/kg	4 mcg/kg	2 mcg/kg	4 mcg/kg
60 kg	0.27	0.51	129.73	249.49	130 ml	250 ml
75 kg	0.33	0.63	159.67	309.37	160 ml	310 ml
90 kg	0.39	0.76	189.61	369.24	190 ml	370 ml
105 kg	0.45	0.88	219.55	429.12	220 ml	430ml

Dose calculation for obese patients:

For patients whose body mass index (BMI) is $>30 \text{ kg/m}^2$, the factor for body weight used in calculating IL-15 doses will be determined as follows:

$$\text{Corrected body weight (kg)} = 30 \times (\text{height [m]})^2$$

16.4 APPENDIX D: ASSAY FOR ANTIBODIES TO rhIL-15

- Plates are coated with human IL-15 for 3 hours at 37°C, washed, blocked with 3% FBS and washed again.
- A standard curve for assay quantitation and quality control is constructed using serial dilutions of a commercial affinity purified goat anti-human IL-15 that is diluted in heat-inactivated normal human serum. The standard curve samples are incubated for 2 hours at 37°C and washed.
- Biotin conjugated IL-15 is added to each well, incubated 2 hours at 37°C, and the plates are washed.
- Alkaline phosphatase-conjugated streptavidin is added to each well for 2 hours at 37°C and then washed.
- The assay is developed with the addition of diethanolamine buffer with p-Nitrophenyl Phosphatase for 1 hour at 37°C and then immediately read at 405 nm.
- To detect antibodies to human IL-15 in test samples, serum from the test subject will be assayed in duplicate at dilutions of 1/3 and 1/9 concomitantly with the standard curve samples as above and the resultant OD obtained used to quantitate the level of antibody present.

16.5 APPENDIX E: MODIFIED IMMUNE-RELATED RESPONSE CRITERIA (irRECIST)

This new classification is based on the recent learning from clinical studies with cancer immunotherapies that even if some new lesions appear at the beginning of a treatment or if the total tumor burden does not increase substantially, tumor regressions or stabilizations might still occur later. The irRC were created using bi-dimensional measurements (as previously widely used in the World Health Organization criteria). For this trial, the concepts of the irRC are combined with RECIST 1.1 to come up with the modified irRC.

For modified irRC, only target and measurable lesions are taken into account. In contrast to the RECIST 1.1 criteria, the modified irRC criteria (a) require confirmation of both progression and response by imaging at 6-8 weeks after initial imaging and (b) do not necessarily score the appearance of new lesions as progressive disease if the sum of lesion diameters of target lesions (minimum of 10 mm per lesion, maximum of 5 target lesions, maximum of 2 per organ) and measurable new lesions does not increase by $\geq 20\%$.

The same method of assessment and the same technique should be used to characterize each identified and reported target lesion(s) at baseline, during the trial, and at the end of trial visit. All measurements should be recorded in metric notation. The modified irRC based on RECIST 1.1 are displayed below.

Modified immune-related response criteria are defined as follows:

New measurable lesions: Incorporated into tumor burden.

New non-measurable lesions: Do not define progression but precludes (irCR).

Overall irCR: Complete disappearance of all lesions (whether measurable or not) and no new lesions. All measurable lymph nodes also must have a reduction in short axis to 10 mm.

Overall irPR: Sum of the longest diameters of target and new measurable lesions decreases $\geq 30\%$.

Overall irSD: Sum of the longest diameters of target and new measurable lesions neither irCR, irPR, (compared to baseline) or irPD (compared to nadir).

Overall irPD: Sum of the longest diameters of target and new measurable lesions increases $\geq 20\%$ (compared to nadir), confirmed by a repeat, consecutive observations at least 4 weeks (normally it should be done at 6 weeks) from the date first documented.

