6.3 RESPONSE CRITERIA

6.3.1 Response Assessments

Tumor response will be assessed radiographically after cycle 2 and 4 treatments are completed by the investigator using the Immune-Modified Response Evaluation Criteria In Solid Tumors, i.e., imRECIST criteria [\[88\]](#) for Immune-related Best Overall Response (irBOR, Section **6.4.1**) will be derived based on reported lesion responses at different evaluation time points from the first trial treatment administration until immune-related disease progression per imRECIST [\[88\]](#) according to the following rules:

- irCR = at least two radiographic determinations of CR at least 4 weeks apart and before irPD
- irPR = at least two radiographic determinations of PR or better at least 4 weeks apart and before irPD (and not qualifying for an irCR)
- irSD = at least one radiographic assessment of SD (or better) ≥ 6 weeks after the first trial treatment administration and before irPD (and not qualifying for irCR or irPR).
- irPD = at least two consecutive radiographic determinations of PD at least 4 weeks apart.

Only tumor assessments performed before the start of any further anti-cancer treatment will be considered in the assessment of irBOR.

Immune-related Objective Response (irOR) is defined as irCR or irPR according to irRECIST from the first trial treatment administration until irPD or death due to any cause. Both irCR and irPR must be confirmed by repeat assessments performed no less than 4 weeks after the criteria for immune-related response are first met. Also, irPD must be confirmed by a second, consecutive assessment at least 4 weeks apart. Immune-related OR rate (irORR) is the proportion of subjects with irOR in the analysis set.

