6.3.7 Evaluation of Best Overall Response

The best overall response is the best response recorded from the start of the treatment until disease progression/recurrence (taking as reference for progressive disease the smallest measurements recorded since the treatment started). The patient's best response assignment will depend on the achievement of both measurement and confirmation criteria.

For Patients with Measurable Disease (i.e., Target Disease)

Target Lesions	Non-Target Lesions	New Lesions	Overall Response	Best Overall Response when Confirmation is Required*
CR	CR	No	CR	≥ 4 wks. Confirmation**
CR	Non-CR/Non-PD	No	PR	
CR	Not evaluated	No	PR	
PR	Non-CR/Non-PD/not evaluated	No	PR	≥ 4 wks. Confirmation**
SD	Non-CR/Non-PD/not evaluated	No	SD	Documented at least once ≥ 4 wks. from baseline**

Target Lesions	Non-Target Lesions	New Lesions	Overall Response	Best Overall Response when Confirmation is Required*
PD	Any	Yes or No	PD	no prior SD, PR or CR
Any	PD***	Yes or No	PD	
Any	Any	Yes	PD	

* See RECIST 1.1 manuscript for further details on what is evidence of a new lesion.
** Only for non-randomized trials with response as primary endpoint.
*** In exceptional circumstances, unequivocal progression in non-target lesions may be accepted as disease progression.
Note: Patients with a global deterioration of health status requiring discontinuation of treatment without objective evidence of disease progression at that time should be reported as “*symptomatic deterioration*.” Every effort should be made to document the objective progression even after discontinuation of treatment.

For Patients with Non-Measurable Disease (i.e., Non-Target Disease)

Non-Target Lesions	New Lesions	Overall Response
CR	No	CR
Non-CR/non-PD	No	Non-CR/non-PD*
Not all evaluated	No	not evaluated
Unequivocal PD	Yes or No	PD
Any	Yes	PD

* ‘Non-CR/non-PD’ is preferred over ‘stable disease’ for non-target disease since SD is increasingly used as an endpoint for assessment of efficacy in some trials so to assign this category when no lesions can be measured is not advised

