10 STATISTICAL CONSIDERATIONS

10.1 STATISTICAL HYPOTHESES

10.1.1 Primary Endpoints

Overall Response (CR + PR) by irRECIST 1.1 criteria in patients who receive at least 1 cycle of therapy with the 4 mcg/kg dose of rhIL-15.

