10.2 SAMPLE SIZE DETERMINATION

The primary objective of this trial is to determine the efficacy of combination treatment of CIV rhIL-15 on days 1-5 and IV anti PDL-1 avelumab on day 8 and 22 of the 28-day cycle in patients with treatment refractory PD-L1+ ($\geq 5\%$) metastatic clear-cell renal carcinoma in terms of overall response. All patients must have failed or relapsed and have progressive disease after at least 2 prior therapies that include multityrosine kinase inhibitor like axitinib or sunitinib and an anti-PD1

or PD-L1 ICI therapy like nivolumab. The primary endpoint will be overall response (OR) per irRECIST 1.1 criteria.

A Simon two stage Simon Optimal Design will be used for the analysis of the primary endpoint of overall response rate. A minimum of 12 (3 in the 2mcg/kg safety run-in cohort (Cohort 1) and 9 evaluable in the first stage) and maximum of 25 patients will be enrolled in order to have 17 evaluable patients treated at the recommended phase 2 dose for the CIV rhIL-15 schedule at dose 4 mcg/kg/day. A maximum of 19 patients may be enrolled in the phase 2 part of this trial to compensate for inevaluable patients. The sample size for this trial is based on the plan for 3 to 6 patients treated in the 2 mcg/kg/day safety run-in cohort and to accurately assess target 25% response rate in the 4 mcg/kg dosing cohort with a power of 80% to determine the feasibility if this rate were true. The overall Type I error was set at 5% and power at 80% that assumes a null hypothesis success rate of 5% versus a treatment with a 25% response rate. Patients treated in the 2 mcg/kg/day safety cohort will not be included in the primary end point analysis but will be included in the safety cohort and be assessed for the secondary endpoints.

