² 30 days (+7) following last dose, and 90 days (+14) after last dose of avelumab (via clinic or phone/email). If initiating new anti-cancer therapy within 30 days after last dose of avelumab, 30-day safety follow-up visit must occur before first dose of new therapy.

³ Screening and Baseline evaluations should be performed within 28 days prior to enrollment and dosing, respectively, unless otherwise noted and with the following exceptions: Confirmation of diagnosis (no time limit); HIV antibody, Hepatitis B surface antigen and Hepatitis C antibody and EKG (all within 3 months) **NOTE:** Any screening tests performed within the specified time frame for baseline do not need to be repeated.

⁴ Within 14 days prior to dosing on C1D1, with the following exceptions: Pregnancy test (within 7 days of dosing; must be negative).

⁵ \pm 2 days. Confirmatory scans should also be obtained 4 weeks following initial documentation of objective response.

⁶ To be done at end of treatment (30 days after last dose of study treatment; may be combined with 30 day safety follow-up, if timing coincides). If subject to initiate new anti-cancer therapy assessments should occur before the first dose of the new therapy.

⁷ Follow-up to occur about every 60 days (\pm 7 days) for first 6 months, every 90 days (\pm 14 days) for 2 years; then every six months (\pm 28 days) for the duration of the study until disease progression or initiation of new anti-cancer therapy.

⁸ After disease progression or initiation of new anti-cancer therapy, contact for survival about every 3 months (± 4 weeks) for the duration of the study after stopping treatment.

⁹ Pathologic review/confirmation of diagnosis by Laboratory of Pathology, NCI (no time limit) and PD-L1 as outlined in Section [5.2.4.1](#). If archival sample is not available, a fresh punch or core biopsy of an appropriate easily accessible tumor deposit will be obtained.

¹⁰ Physical exams to include medical history (i.e., complete at Screening/Baseline; interim on study and in follow-up), vitals, weight, and height (screening only).

¹¹ Chemistry panels include: Acute care, Hepatic, and Mineral.

¹² Diffusing capacity/alveolar volume (DLCO/VA), forced expiratory volume in 1 second (FEV1) for patients with significant pulmonary or smoking history or suspected tumor related pulmonary dysfunction and Transthoracic Echocardiograph for patients with suspected cardiac dysfunction that would increase their risk in receiving protocol treatment.

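### Appendix E confirms response at 6–8 weeks, while 6.3.1, 6.3.7 and the study calendar work to a 4-week minimum, so the same scans can be classified two ways on the primary endpoint

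*Combined protocol and SAP*

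**What the plan says.** **Endpoint.** Section 10.1.1 names "Overall Response (CR + PR) by irRECIST 1.1 criteria in patients who receive at least 1 cycle of therapy" at the 4 mcg/kg dose, and section 10.2 repeats it: "The primary endpoint will be overall response (OR) per irRECIST 1.1 criteria". Neither gives a confirmation interval.

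**Appendix E.** Section 6.4 says irRECIST is also used in this study and refers to Appendix E for further detail. Appendix E states that, unlike RECIST 1.1, its criteria "require confirmation of both progression and response by imaging at 6-8 weeks after initial imaging". Its list of definitions gives no interval for irCR or irPR. For irPD it gives at least 4 weeks, normally 6.

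**Section 6.3.1.** "Both irCR and irPR must be confirmed by repeat assessments performed no less than 4 weeks after the criteria for immune-related response are first met". The rule for a partial response is consistent with this: "irPR = at least two radiographic determinations of PR or better at least 4 weeks apart".

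**Section 6.3.7.** The best-response table asks for "≥ 4 wks. Confirmation" for both CR and PR.

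**Study calendar (Appendix F), footnote 5.** "Confirmatory scans should also be obtained 4 weeks following initial documentation of objective response".

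**Section 10.3.2.** Response is to be classified by the definitions in Section 6.3.

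**The concern.** The section that 6.4 cites for the irRECIST criteria requires one confirmation interval. The section that defines immune-related objective response, together with the calendar that tells the site when to scan, uses another. A site that follows the calendar obtains a confirmatory scan that is valid under 6.3.1 and too early for Appendix E.

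Response decides whether the trial succeeds (at least 3 of 17). The trial is open-label and the investigator assesses response. If two written confirmation rules remain in force, a borderline patient's status could be settled after the scans have been seen. With a boundary of 3 responders, one such patient can change the reported conclusion.

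**Working it through.** **1. The rules in days after the first response scan**

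| Source | Requirement | Days |
|---|---|---|
| Appendix E | 6–8 weeks | 6 × 7 = 42 to 8 × 7 = 56 |
| 6.3.1 and 6.3.7 | at least 4 weeks | 28 or later, no upper limit |
| Calendar footnote 5 | scan at 4 weeks | about 28 |

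The scheduled confirmatory scan falls 42 − 28 = 14 days before the Appendix E window opens. Any confirmation inside days 42–56 also meets the 28-day minimum. The rules therefore diverge only when confirmation rests on a scan before day 42 or after day 56, and in both cases Appendix E is the stricter.

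**2. A patient classified two ways.** With 28-day cycles, the scan after cycle 2 is at about day 56 and the scan after cycle 4 at about day 112.

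- Day 56: PR first seen.
- Day 84 (28 days later): PR on the footnote 5 scan.
- Day 112 (56 days later): response lost.

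Under 6.3.1 there are two PR determinations 28 days apart, so this is a confirmed irPR. Under Appendix E the window is days 98–112 (56 + 42 to 56 + 56), and the only scan in it shows no response, so the response is unconfirmed.

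**3. Is a scan available in the Appendix E window?**

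- Response first seen after cycle 2: the next planned evaluation is 56 days later, or 52–60 days with ±2 days on each scan. It is usually inside 42–56 but can fall past it.
- Response first seen after cycle 4: the next visit after the 4-week scan is the 60-day (±7) follow-up, which section 3.6.3 counts from the end of treatment. Counted from the last avelumab dose (cycle 4 day 22, i.e. 84 + 22 = day 106), it falls on day 166 (159–173), which is 54 days (47–61) after a day-112 scan. Counted from day 112 itself, it is 60 days (53–67) after that scan. The calendar marks imaging at this visit, but 3.6.3 also allows other clinical assessments. A scan in the window is possible but not assured.

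**4. The plan's own design figures.** Section 10.2 gives 9 then 17 patients, continuing with at least 1 of 9 and succeeding with at least 3 of 17, for 5% versus 25%.

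- Stop at Stage 1 under the null: 0.95⁹ = 0.630 (stated 63%).
- At least 1 of 9 at 25%: 1 − 0.75⁹ = 0.925 (stated 92%).
- Chance of success at rate p: Σ over x = 1…9 of C(9,x) pˣ(1−p)⁹⁻ˣ × P[Bin(8,p) ≥ 3 − x]. This gives 0.812 at 25% (stated power 80%) and 0.047 at 5% (stated limit 5%).

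The stated figures reproduce.

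**5. How often one patient is decisive**

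- Exactly 1 responder among 9: 9p(1−p)⁸ = 22.5% at p = 25% and 29.9% at p = 5%.
- Passing Stage 1 and ending with exactly 3 of 17: [C(17,3) − C(8,3)] p³(1−p)¹⁴ = 624 p³(1−p)¹⁴ = 17.4% at 25% and 3.8% at 5%.

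**6. Illustration with an assumed loss.** Let f be the share of 4-week-confirmed responses not confirmed at 6–8 weeks. The documents give no value for f. The calculation applies one rule at both stages.

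| f | Rate under Appendix E if the 4-week rate is 25% | Chance of success | 4-week rate if the Appendix E rate is 5% | Type I error counting by 4 weeks |
|---|---|---|---|---|
| 0 | 0.250 | 81.2% | 0.0500 | 4.7% |
| 10% | 0.225 | 74.5% | 0.0556 | 6.0% |
| 20% | 0.200 | 66.3% | 0.0625 | 8.0% |
| 30% | 0.175 | 56.6% | 0.0714 | 10.9% |

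The second column is 0.25(1 − f) and the fourth is 0.05/(1 − f).

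**The case against.** The best defence is that the plan already shows which rule it means. Section 10.3.2 sends classification to Section 6.3. Section 6.3.1 defines objective response as an irRECIST response with a 4-week minimum, 6.3.7 agrees, and the calendar schedules the scan to match. The 6–8 week phrase stands in Appendix E's introductory comparison with RECIST 1.1, not in its list of definitions, and the irPD definition there already departs from it. It may be leftover description.

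Much of this stands: the 4-week minimum is the better-supported reading, and a reader who infers that the investigator may freely pick either rule goes further than the text allows. It does not remove the conflict. The endpoint is named irRECIST, 6.4 assigns irRECIST to Appendix E, and 6.3.1 itself mixes imRECIST and irRECIST. No section gives 6.3 precedence or withdraws the 6–8 week requirement, which Appendix E presents as a deliberate difference from RECIST 1.1.

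Three other stronger inferences also fail:

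- That the rules exclude each other. Four weeks is a minimum, so a response seen again at 6–8 weeks satisfies both.
- That no scan can fall in the window after cycle 4. The 60-day follow-up may do so.
- That confirmed response already governs both Simon stages. The Stage 1 gate in 10.2 is worded as a reduction of more than 20% in tumour volume, with no confirmation interval.

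**Conclusion.** Wrong as written. Current text sets two confirmation intervals for the primary endpoint, and the scheduled confirmatory scan meets one and misses the other by about 14 days. The affected patients are those whose response is confirmed at 4 weeks but not by a scan at 6–8 weeks, including any for whom no scan falls in that window.

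Two findings are firm: the same scans can be classified two ways, and one patient can separate 3 of 17 from 2 of 17. The fall in the chance of success from 81% to 75%, 66% or 57%, and the corresponding rise in type I error, are illustrations. They rest on assumed values of f and on one rule being enforced at both stages. A reader might take them as the power this trial will have, but the documents do not support that: under the 4-week minimum, which 10.3.2 favours, power stays at 81%. The Simon design figures are correct.

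**What to change.** 1. **Appendix E, response only:** replace the 6–8 week interval with a minimum of 4 weeks from the date the response criteria are first met, matching 6.3.1, 6.3.7 and calendar footnote 5.
2. **Section 10.1.1:** state that the primary endpoint is confirmed irCR or irPR as defined in 6.3.1.
3. **Section 10.2:** reword both Stage 1 references to a 20% reduction in tumour volume so that they use the same response definition. Without this, one rule does not serve both Simon stages.
4. **Progression, separately:** the sponsor must reconcile the progression-confirmation intervals, which are 6–8 weeks and at least 4 (normally 6) weeks within Appendix E, and at least 4 weeks in 6.3.1.

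The cost is a wording amendment to Appendix E, 10.1.1 and 10.2, plus the sponsor's decision on item 4. Items 1–3 add no scans, because footnote 5 already schedules the 4-week scan, and the sample size does not change.

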6.3.5 Evaluation of Target Lesions

Complete Response (CR): Disappearance of all target lesions. Any pathological lymph nodes (whether target or non-target) must have reduction in short axis to <10 mm.

Partial Response (PR): At least a 30% decrease in the sum of the diameters of target lesions, taking as reference the baseline sum diameters.

Progressive Disease (PD): At least a 20% increase in the sum of the diameters of target lesions, taking as reference the smallest sum on study (this includes the baseline sum if that is the smallest on study). In addition to the relative increase of 20%, the sum must also demonstrate an absolute increase of at least 5 mm. (Note: the appearance of one or more new lesions is also considered progressions).

Stable Disease (SD): Neither sufficient shrinkage to qualify for PR nor sufficient increase to qualify for PD, taking as reference the smallest sum diameters while on study.

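### Appendix E defines irPD as a confirmed 20% rise over nadir but leaves out the 5 mm minimum of Section 6.3.5, which exposes small tumor sums (nadir below 25 mm) to false progression

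*Combined protocol and SAP*

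**What the plan says.** The primary endpoint is response by irRECIST (Sections 10.1.1 and 10.2). Section 6.3.1 counts an irCR or irPR only if it is established before irPD. Appendix E (16.5) is where irPD is given a size threshold. It reads "Overall irPD: Sum of the longest diameters of target and new measurable lesions increases", with the threshold set at 20% or more over nadir. The same sentence requires that the rise be "confirmed by a repeat, consecutive observations at least 4 weeks (normally it should be done at 6 weeks) from the date first documented", and Section 6.3.1 agrees: "Also, irPD must be confirmed by a second, consecutive assessment at least 4 weeks apart".

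Section 6.3.5 has a second condition for RECIST progression: "In addition to the relative increase of 20%, the sum must also demonstrate an absolute increase of at least 5 mm".

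Appendix E introduces its differences this way: "In contrast to the RECIST 1.1 criteria, the modified irRC criteria (a) require confirmation of both progression and response". Its second listed difference, (b), concerns new lesions. The millimetre minimum appears in neither. Section 6.4 and Appendix E both describe the criteria as a combination with RECIST 1.1, without saying whether the 5 mm condition carries over.

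Three other places bear on the point:

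- Sections 6.3.8 and 10.4.2 (duration of response) and 6.3.11 (PFS) end at progression, without naming irPD or RECIST PD.
- Section 6.3.9 gives a separate rule for progression after PR or SD. It includes a 20% rise from nadir in the size of other lesions, with no 5 mm minimum.
- Section 2.1.1.3 admits patients with a single measurable lesion, and Section 6.3.3 sets measurability at 10 mm on CT.

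**The concern.** On a small tumor sum, 20% is only a few millimetres, which may lie within reading error. RECIST's absolute minimum guards against this, and the plan keeps it in Section 6.3.5 but not in the immune-related rule. Taken literally, Appendix E can record confirmed progression in a patient whose tumor has not grown.

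The patients exposed are those with little tumor at nadir, a group that includes good responders. Responders supply all the duration-of-response data, and there may be few of them: Section 10.2 calls the treatment worthy of further study with 3 responses in 17. With 3 responders, one misdated progression would affect a third of that data, if irPD is the event that ends duration of response.

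The same scans can also give two different progression dates under two rules in the same plan, and nothing says which date counts.

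**Working it through.** No figure in the plan depends on this rule, so there is none to reproduce.

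**Inputs from the documents**

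- irPD: at least 20% over nadir, confirmed on a consecutive scan (Appendix E).
- RECIST PD: at least 20% over nadir and at least 5 mm (6.3.5).
- Lesions: "minimum of 10 mm per lesion, maximum of 5 target lesions, maximum of 2 per organ" (Appendix E); one measurable lesion suffices for entry (2.1.1.3).
- Partial response: a fall of at least 30% from baseline (6.3.5, Appendix E).
- Imaging: after cycles 2 and 4, then every 60 days for 6 months and every 90 days for 2 years (3.6.3, Appendix F).

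**Inputs assumed, because the documents do not give them**

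- SD of reading error of the sum: 1, 1.5 and 2 mm, with 0.5 mm as a check.
- True sum constant after nadir; errors normal and independent between scans.
- Number of later scans: 3 or 6. Six corresponds to the scan after cycle 4, three at 60-day intervals and two at 90-day intervals.

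**Step 1: where the rules differ.** The 5 mm condition matters when 0.20 × nadir < 5, that is, nadir < 25 mm. For a responder with exactly a 30% fall, nadir = 0.70 × baseline, so the baseline sum is below 25 / 0.70 = 35.7 mm. Deeper responses reach this range from larger baselines: 60 mm reduced by 60% is 24 mm. At nadirs of 10, 15 and 20 mm the Appendix E threshold is a rise of 2, 3 and 4 mm.

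**Step 2: what confirmation achieves at one event.** Observed sum = true sum + error. The nadir is the lower of two earlier scans, followed by one event scan and one confirming scan against the same nadir. SD 1.5 mm, 400,000 runs:

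| True sum | 20%, unconfirmed | 20%, confirmed (Appendix E) | 20% and 5 mm, confirmed |
|---|---|---|---|
| 10 mm | 31.8% | 17.2% | 0.2% |
| 15 mm | 17.3% | 7.2% | 0.2% |
| 20 mm | 7.9% | 2.4% | 0.2% |
| 30 mm | 1.0% | 0.1% | 0.1% |

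Confirmation removes a good part of the false events, but not all. One reason is that both scans are compared with the same nadir, which noise has already pulled down.

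**Step 3: accumulation over follow-up.** Running nadir = lowest earlier observed sum. A scan is flagged if it is at least 1.2 × nadir (and, with the minimum, at least 5 mm above it). irPD is scored when two consecutive scans are flagged. True sum 10 mm, 400,000 runs per cell:

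| Later scans | Rule | SD 1 | SD 1.5 | SD 2 |
|---|---|---|---|---|
| 3 | 20%, confirmed | 9% | 21% | 29% |
| 3 | with 5 mm | 0% | 0.3% | 2% |
| 6 | 20%, confirmed | 28% | 54% | 68% |
| 6 | with 5 mm | 0% | 1% | 8% |

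Over 6 scans at a 15 mm sum, the 20% rule gives 7%, 28% and 47%. At 20 mm it gives 1%, 11% and 28%. With the minimum, both sums give 0%, 1% and 8%.

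**Step 4: sensitivity at 10 mm over 6 scans.** At SD 0.5 mm the confirmed false irPD rate is 0.9%. With an assumed correlation of 0.5 between the errors of different scans, the 20% rule gives 9%, 33% and 51% at SD 1, 1.5 and 2 mm.

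**The case against.** The strongest reply has four parts.

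1. **irPD is not a bare 20% rise.** A reader who stops at the threshold might infer that a single misreading of 2-4 mm is scored as progression. It is not: the same sentence of Appendix E, and Section 6.3.1, require a second consecutive scan. This stands, and every headline figure here includes confirmation.

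2. **The 5 mm rule may carry over silently.** Appendix E does not say that its two listed contrasts are the only ones, and it presents itself as a combination with RECIST 1.1. The missing minimum may be shorthand. That is a fair reading, but a scorer working from the Appendix E definitions would not apply a condition that is absent from them. Section 6.3.1 also points to imRECIST, a cited source outside these documents, so the documents alone cannot settle the matter.

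3. **Duration of response and PFS may be untouched.** A reader might infer that both are shortened. The documents do not establish that. Sections 6.3.8, 6.3.11 and 10.4.2 speak only of progression, and two of these sit in the same section as the RECIST definition that contains the minimum. If that definition governs, the effect is nil. If irPD governs, the risk calculated above applies. The plan does not say which.

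4. **The size is assumption-driven.** The documents give no reading error and no distribution of tumor sums. SD 2 mm on a 10 mm sum is a 20% error. Up to five lesions are summed, so a 10 mm total is an extreme case, and how many of the 17 patients would have a nadir below 25 mm is unknown. All of this stands. It limits what can be claimed about magnitude but does not remove the gap between the two definitions.

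**Conclusion.** The point holds as an unreconciled endpoint definition with a conditional consequence. Appendix E omits a condition that Section 6.3.5 imposes and does not announce the omission. The rules differ only for observed nadir sums below 25 mm. In that range confirmation is partial protection: at a stable 10 mm sum, confirmed false irPD is about 9-29% over 3 later scans and 28-68% over 6, against 0-2% and 0-8% with the minimum. These figures rest on assumed independent errors with SD 1 to 2 mm. They fall as the sum grows, and at SD 0.5 mm they are under 1%.

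Two stronger readings are not supported:

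- **That responders would be taken off therapy.** On the nominal schedule a response is first seen after cycle 2 (week 8), and its confirming scan falls at week 12. A rise first seen there could be confirmed no earlier than week 16, when four 28-day cycles are complete. Section 6.3.2 also allows treatment beyond radiographic progression.
- **That the primary response rate is biased.** Section 6.3.1 does require response before irPD, but no effect on the response rate or on the two-stage test has been shown. The 9- and 17-patient boundaries are unaffected.

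**What to change.** For endpoint scoring only:

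- In Appendix E, keep the confirmation requirement and add to irPD that the sum must also rise by at least 5 mm over nadir. Add the same condition to clause (b) on new measurable lesions. If leaving out the minimum was deliberate, say so and give the reason.
- Reconcile Sections 6.3.5 and 6.3.9 with Appendix E, so that one progression rule applies after a response. Editing Appendix E alone would leave the 20% rule in 6.3.9 without the minimum. Appendix E's own confirmation intervals also need reconciling: at least 4 weeks in the irPD definition, but elsewhere "require confirmation of both progression and response by imaging at 6-8 weeks after initial imaging".
- In Sections 6.3.8, 6.3.11 and 10.4.2, name the progression definition that ends duration of response and PFS.

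The cost is a few clauses of text. No new data are needed, and the sample size and stage boundaries do not change. The downside is that true progression from a very small nadir may be dated one scan later.
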